10.11.4 Week 2 (Visit 3a)

The following assessments will be performed at Week 2 (\pm 3 days) after initial treatment:

- Urine pregnancy test in women of childbearing potential only, including those who are postmenopausal for less than twelve months (in case of touch-up only and then prior to treatment)
- Body weight measurement
- In case of touch-up treatment, visual examinations (including Snellen visual acuity, confrontational visual fields and ocular motility). prior to- and 30 min after treatment. For action to be taken in case of abnormal findings, see Section 10.8.4.
- Treatment (touch-up) if needed
- Collect and review of subject diary dispensed at Baseline (Visit 2)
- Dispense of new subject diary
- Assessment of injection volume (in case of touch-up)
- AEs (prior to treatment)
- Concomitant medications/procedures (prior to treatment)

10.11.5 Phone Contact after Visit 3a

The following assessments will be performed at Day 3 (± 24 hours) after Visit 3a:

- AEs including if subjects are experiencing or have experienced any signs/symptoms of vision changes or stroke since the injection
- Concomitant medications/procedures

10.11.6 Week 4 (Visit 3b)

The following assessments will be performed at Week 4 (\pm 5 days) after initial treatment:

- Body weight measurement
- Visual examinations (including Snellen visual acuity, confrontational visual fields and ocular motility). For action to be taken in case of abnormal findings, see Section 10.8.4.
- Collect and review of subject diary dispensed at Week 2 (Visit 3a)
- Dispense of new subject diary (only in case touch-up treatment occurred at Week 2/Visit 3a)
- AEs
- Concomitant medications/procedures

10.11.7 Week 6 (Visit 3c)

The following assessments will be performed at Week 6 (\pm 5 days) after initial treatment:

- Body weight measurement
- In case touch-up was performed at Week 2 (Visit 3a), visual examinations (including Snellen visual acuity, confrontational visual fields and ocular motility). For action to be taken in case of abnormal findings, see Section 10.8.4.
- Collect and review of subject diary dispensed at Week 4 (Visit 3b)
- AEs
- Concomitant medications/procedures

10.11.8 Week 12 (Visit 4) and Week 24 (Visit 5)

The following assessments will be performed at Week 12 (\pm 5 days) and Week 24 (\pm 5 days) after initial treatment:

- Body weight measurement
- Live assessment of nasolabial fold severity by treating investigator using NLF-SRS
- Live assessment of nasolabial fold severity by the independent blinded evaluating investigator using NLF-SRS
- Assessment of GAIS over Baseline by the evaluating investigator and the subject
- Face-Q subject appearance appraisal questionnaire ("appraisal with nasolabial folds")

- Face-Q subject satisfaction ("Satisfaction with Outcome")
- Photography
- AEs
- Concomitant medications/procedures

10.11.9 Week 36 (Visit 6) and/or Week 48 (Visit 7) and/or Visit 7c - Evaluation

A repeat-treatment will be performed, if the subject meets the criteria specified in Section 9.2.

The following assessments will be performed at evaluation for repeat-treatment at Week 36 (\pm 5 days) and/or Week 48 (\pm 5 days) after initial treatment and/or Visit 7c (no visit window):

- Body weight measurement
- Eligibility for repeat-treatment (see Section 9.2)
- Urine pregnancy test in women of childbearing potential only, including those who are postmenopausal for less than twelve months
- Live assessment of nasolabial fold severity by treating investigator using NLF-SRS
- Live assessment of nasolabial fold severity by the independent blinded evaluating investigator using NLF-SRS
- Assessment of GAIS over Baseline by the independent blinded evaluating investigator and the subject
- Face-Q subject satisfaction ("Satisfaction with Outcome")
- FACE-Q subject appearance appraisal questionnaire ("Appraisal with Nasolabial Folds")
- Photography
- AEs
- Concomitant medications/procedures

Some subjects were not assessed for repeat-treatment at Week 36 and/or Week 48 due to the hold on repeat-treatment. In this case, a subject can attend Visit 7c (no visit window) for evaluation and repeat-treatment as described above (if eligible).

10.11.10 Week 36 (Visit 6) and/or Week 48 (Visit 7) and/or Visit 7c - Repeat-

Treatment

The following assessments will be performed at Week 36 (\pm 5 days) and/or Week 48 (\pm 5 days) after initial treatment and/or at Visit 7c (no visit window):

- In case of repeat-treatment at Week 36 (Visit 6), Week 48 (Visit 7) or Visit 7c, visual examinations (including Snellen visual acuity, confrontational visual fields and ocular motility) prior to- and 30 min after the treatment. For action to be taken in case of abnormal findings, see Section 10.8.4.
- Treatment
- Evaluation of pain assessment by the subject using the adapted NPRS
- Dispense of subject diary
- Assessment of injection volume

If the subject is being retreated at Week 36, subject qualifies for 4 Weeks Follow up after repeat-treatment at Week 40. If the subject is being retreated at Week 48, subject qualifies for 4 Weeks Follow up after repeat-treatment at Week 52. If the subject is being retreated at Visit 7c, subject qualifies for 4 Weeks Follow up after repeat-treatment at Visit 8c.

10.11.11 Phone Contact after Visit 6, Visit 7 or Visit 7c

The following assessments will be performed at Day 3 (\pm 24 hours) after Visit 6, Visit 7 or Visit 7c, if the subject received a repeat-treatment:

- AEs including if subjects are experiencing or have experienced any signs/symptoms of vision changes or stroke since the injection
- Concomitant medications/procedures

10.11.12 Week 40 (Visit 8a), Week 52 (Visit 8b) or Visit 8c

The following assessments will be performed at the end of clinical investigation visit at Week 40 (\pm 5 days), Week 52 (\pm 5 days) or Visit 8c (\pm 5 days), which are four weeks after repeat-treatment:

- In case repeat-treatment was performed at Week 36 (Visit 6) or Week 48 (Visit 7) or Visit 7c, visual examinations (including Snellen visual acuity, confrontational visual fields and ocular motility). For action to be taken in case of abnormal findings, see Section 10.8.4.
- Body weight measurement
- Collect subject diary dispensed at repeat-treatment (Visit 6, Visit 7 or Visit 7c)
- AEs
- Concomitant medications/procedures

If the subject is not being treated at Week 36, no Week 40 Visit is necessary.

10.11.13 Week 48 (Visit 9a), Week 60 (Visit 9b) or Visit 9c

The following assessments will be performed at the end of clinical investigation visit at Week 48 (\pm 5 days), Week 60 (\pm 5 days) or Visit 9c (\pm 5 days), which are twelve weeks after repeat-treatment:

- In case repeat-treatment was performed at Week 36 (Visit 6), Week 48 (Visit 7) or Visit 7c, visual examinations (including Snellen visual acuity, confrontational visual fields and ocular motility). For action to be taken in case of abnormal findings, see Section 10.8.4.
- Body weight measurement
- AEs
- Concomitant medications/procedures

For subjects who are not retreated at Week 36 (Visit 6) or Week 48 (Visit 7), the Week 48 Visit will be their end of study visit unless the subject returns for Visit 7c. For subjects who are not retreated at Visit 7c, Visit 7c will be their end of study visit. For subjects who are retreated at Week 36, the Week 48 Visit will be their end of study visit. For subjects who are retreated at Week 48, the Week 60 Visit will be their end of study visit. For subjects who are retreated at Visit 7c, Visit 9c (12 weeks after Visit 7c) will be their end of study visit.

10.12 Early Termination

In case a subject prematurely discontinues the clinical investigation, the subject will be asked to complete an early termination visit, where as many assessments as possible (which would normally be performed at the end of clinical investigation visit at Week 48, Week 60 or Visit 9c)

STRICTLY CONFIDENTIAL

CPH-301-201200F

will be completed. If an early termination visit can't take place, the investigator or any member of the clinical investigation team should try to contact the subject, or his relatives, in order to collect adverse events and concomitant medications/treatments.

In case of early withdrawal, reasons, as well as circumstances and findings, should be collected and fully described on the "Early Termination" page in the eCRF.

10.13 Time-Windows

A time deviation of \pm 5 days is allowed for each visit, except for phone contacts (+/- 24 hours) and for the touch-up visit at Week 2 (+/- 3 days). Clinical investigational sites must adhere to the Schedule of Clinical investigation Procedures and Assessments (see Section 2.1) and visit windows, and subjects must ensure they are available for those visits. However, if for practical reasons, e.g. bank holidays, a visit window cannot be met, a visit can be scheduled as close as possible to that visit window. However, any deviation from the visit schedule and its associated time windows will still be documented as a protocol deviation.

10.14 Medical Care upon Termination of the Clinical Investigation

Clinical investigation subjects will not receive any clinical investigation-specific treatment after the final visit. Any further treatment, if needed, will be proposed to the subject by the investigator at their discretion. After the final visit, subjects will not receive any further clinical investigation-specific treatment. 15 Mar 2021

11 Monitoring Plan

The extent of monitoring and source data verification will be specified in a monitoring plan. 100% source data verification should be ensured in accordance to the monitoring plan.

Before clinical investigation initiation at a center, a clinical research associate (CRA) from the sponsor or sponsor's representative will discuss the CIP and eCRF with the treating investigators and their staff. The center must not enroll any subject before this initiation visit. During the clinical investigation, further monitoring visits will be performed according to ISO 14155:2011, the applicable standard operating procedures (SOP), and local regulations. The eCRFs will be reviewed against source data in accordance to the monitoring plan for adherence to the CIP, as well as for completeness, accuracy and consistency of data. Additionally, the CRA will check the progress of enrollment, and will ensure that the investigational device is stored, dispensed and accounted for according to respective specifications. Key clinical investigation personnel must be available to assist the CRA during these visits. The CRA informs the treating investigator or authorized designee of any eCRF entry error, omission, or illegibility. The CRA should ensure that appropriate corrections, additions, or deletions are made, dated, explained (if necessary), and initialed by the treating investigator or by an authorized designee.

The treating investigators must permit the monitors access to those portions of the subject's primary medical records, which directly concern this clinical investigation.

It is the treating investigator's obligation to assure documentation of all relevant data in the subject's file, such as medical/aesthetic procedures history and concomitant diseases, date of enrollment into the clinical investigation, visit dates, results of examinations, application of medical device, and AEs and ADEs.

12

Assessment of Safety

12.1 Definitions of Adverse Events and Adverse Device Effects

Adverse Event (AE)

An AE is defined as any untoward medical occurrence, unintended disease or injury or any untoward clinical signs in subjects, users or other persons. This definition includes events whether or not related to the IMDs and those events related to the procedures involved.

Adverse Device Effect (ADE)

An ADE is defined as an AE that is related to the use of the IMDs. This includes any AE resulting from insufficiencies or inadequacies in the IFU, the deployment, the implantation, the installation, the operation, or any malfunction of the IMDs. In addition, this includes any event that is a result of a use error or intentional misuse of the IMDs.

Those AEs occurring after provision of informed consent and prior to application of the IMDs will be recorded as part of the medical/aesthetic procedures history. Any medical condition that is present at the time that the subject is screened should be also considered as medical/aesthetic procedures history and not recorded as an AE (see Section 10.9). However, if the condition deteriorates at any time from date of administration of the IMDs during the clinical investigation, it should be recorded and reported as an AE.

For a list of anticipated AEs and anticipated ADEs please refer to Section 6.1. In addition, the following events could specify as Adverse Events of Special Interest (AESI);

- Changes in vision (i.e. loss of vision, blurriness, double vision, pain in or around your eye, blindness, blind spots, problems moving the eyes, change in peripheral vision)
- Skin changing color around the eyelids or around the site of injection

Serious Adverse Event (SAE)

An SAE is defined as an AE meeting one or more of the following conditions:

- led to death
- led to serious deterioration in health of the subject that either resulted in:
 - o a life-threatening illness or injury, or

- o a permanent impairment of a body structure or a body function, or
- o in subject hospitalization or prolonged hospitalization, or
- o medical or surgical intervention to prevent life-threatening illness or injury or permanent impairment to a body structure or a body function
- led to fetal distress, fetal death, or a congenital abnormality or birth defect
- is an important medical event

Note: Medical or scientific judgment should be exercised in deciding whether reporting is appropriate in other situations, such as important medical events that may not be immediately life threatening or result in death or require hospitalization, but may jeopardize the subject or may require medical or surgical intervention to prevent one of the other outcomes listed in the definitions above. Examples of such events are: invasive or malignant cancers, intensive treatment in an emergency room or at home for allergic bronchospasm, blood dyscrasias, or convulsions that do not result in hospitalization, or development of drug dependence or drug abuse. Hospitalization is defined as at least one overnight stay. Pre-planned hospitalizations (known already prior to signing the ICF) will not be considered an SAE, unless any of the above criteria are fulfilled over the course of the hospitalization due to unplanned complications.

A planned hospitalization for pre-existing condition, or a procedure required by the CIP, without a serious deterioration in health, is not considered to be an SAE.

Serious Adverse Device Effect (SADE)

A serious adverse device effect (SADE) is defined as an ADE that has resulted in any of the consequences characteristic of an SAE.

Unanticipated Adverse Device Effect (UADE)

An unanticipated adverse device effect (UADE) is defined as "any serious adverse effect on health or safety or any life-threatening problem or death caused by, or associated with, a device, if that effect, problem, or death was not previously identified in nature, severity, or degree of incidence in the investigational plan or application (including a supplementary plan or application), or any other unanticipated serious problem associated with a device that relates to the rights, safety, or welfare of subjects" (21 Code of Federal Regulations [CFR] 812.3[s]).

Investigators should report UADEs to the sponsor and to the IRB as follows: Investigators are required to submit a report of a UADE to the sponsor and the reviewing IRB as soon as possible, but in no event later than 10 working days after the investigator first learns of the event (21 CFR 812.150[a]).

Sponsors must immediately conduct an evaluation of a UADE and must report the results of the evaluation to FDA, all reviewing IRBs, and participating investigators within 10 working days after the sponsor first receives notice of the effect (21 CFR 812.46[b], 21 CFR 812.150[b]).

12.2 Documentation of Adverse Events

For each AE, the following must be reported: the date of onset, description of event (event term), event status or date of resolution, severity, action taken (none, medical and/or surgical), relationship to investigational device, relationship to procedure, and seriousness criteria. Each AE must be reported separately. The treating investigator must record all AEs on the "AE" page of the CRF. For SAEs, the Serious Adverse Event Form must also be completed. A complete description of all AEs must also be available in the source documents.

AEs (or ADEs or SADEs) occurring after provision of informed consent and prior to application of the IMDs will be recorded as part of the medical /aesthetic procedures history. Any medical condition that is present at the time that the subject is screened should also be considered as medical/aesthetic procedures history (see Section 10.9) and not recorded as an AE (or ADE or SADE). However, if the condition deteriorates at any time during the clinical investigation from the date of administration of the IMDs, it should be recorded and reported as an AE.

In case the severity or seriousness of an AE changes, the most severe intensity or seriousness of the AE will be recorded and included in the analysis. Separate AEs will not be recorded for each intensity level.

Changes in the assessment of relationship to the IMDs or procedure should also be clearly documented.

Any medication necessary for the treatment of an AE must be recorded on the "Concomitant Medication" page of the CRF.

12.3 Assessment of Adverse Events

All AEs will be assessed in terms of seriousness, severity, outcome, relationship to the IMDs and relationship to procedures.

12.3.1 Assessment of Causality

Investigator is obligated to estimate the relationship between each AE/SAE and the IMD or clinical investigation procedure. Clinical judgment should be used and the relevant documents (e.g., IFU) consulted. The presence of confounding factors, such as concomitant medications/treatments, the natural history of the underlying disease and/or other concurrent illness or risk factors, shall also be considered. This has to be documented within the source data accordingly. The type of relationship should be determined using one of the following causality levels:

Definitely related:

The AE/SAE is associated with the investigational device or with procedures beyond reasonable doubt when:

- the AE/SAE is a known side effect of the product category the device belongs to, or of similar devices and procedures
- the AE/SAE has a temporal relationship with investigational device use/application or procedures
- the AE/SAE involves a body-site or organ that the investigational device or procedures are applied to or have an effect on
- o the AE/SAE follows a known response pattern to the medical device (if the response pattern is previously known)
- the discontinuation of medical device application (or reduction of the level of exposure), when clinically feasible, and reintroduction of its use (or increase of the level of exposure) impact on the event
- o other possible causes (e.g. an underlying or concurrent illness/clinical condition or/and an effect of another device, drug or treatment) have been adequately ruled out
- o harm to the subject is due to error in use

• Probably related:

The relationship with the use of the investigational device seems relevant and/or the event cannot reasonably be explained by another cause, but additional information may be obtained.

• Possibly related:

The relationship with the use of the investigational device is weak, but cannot be ruled out completely. Alternative causes are also possible (e.g. an underlying or concurrent illness/clinical condition or/and an effect of another device, drug or treatment). Cases where relatedness cannot be assessed, or no information has been obtained, should also be classified as possible.

Unlikely related:

The relationship with the use of the device seems not relevant and/or the event can be reasonably explained by another cause, but additional information may be obtained.

• Not related:

Relationship to the device or procedures can be excluded when:

- the AE/SAE is not a known side effect of the product category the device belongs to or of similar devices and procedures
- the AE/SAE has no temporal relationship with the use of the investigational device or the procedures
- o the AE/SAE does not follow a known response pattern to the medical device (if the response pattern is previously known) and is biologically implausible
- o the discontinuation of medical device application or the reduction of the level of exposure (when clinically feasible) and reintroduction of its use (or increase of the level of exposure) do not impact on the event
- the AE/SAE involves a body-site or an organ not expected to be affected by the device or procedure
- the AE/SAE can be attributed to another cause (e.g. an underlying or concurrent illness/ clinical condition, an effect of another device, drug, treatment or other risk factors)

o harm to the subject are not clearly due to use error

The treating investigator will use his/her clinical judgment to determine the relationship. Alternative causes, such as natural history of the underlying diseases, concomitant therapy, other risk factors, and the temporal relationship of the event to the IMD administration will be considered and investigated. The treating investigator will also consult the IFU in the determination of his/her assessment.

If there is a disagreement between Sponsor and Investigator, queries will be sent in an attempt to reach a resolution. The queries will include a statement providing the rationale for the Sponsor assessment causality. Consequentely, a request for the rationale for the Investigator causality will be requested and a confirmation of their causality assessment.

In instances where there is a discrepancy in causality between the Investigator and the reviewing medic, for the causality of the event to the study device. The event will be considered as being related to the study device for the purposes of reporting.

12.3.2 Assessment of Severity

The following definitions for rating severity will be used:

- Mild: The AE is easily tolerated and does not interfere with daily activity
- Moderate: The AE interferes with daily activity but the subject is still able to function
- Severe: The AE is incapacitating and/or requires medical intervention

12.3.3 Adverse Event Outcome

The outcome of an AE will be assessed as follows:

- Ongoing: the event is ongoing at the time of reporting and the subject has still not recovered
- **Resolved:** the subject has fully recovered from the event, or the condition has returned to the level observed at Baseline
- **Resolved with Sequelae:** as a result of the AE, the subject suffered persistent and significant disability/incapacity (e.g. became blind, deaf or paralyzed)

Death: the subject died due to the event

• Unknown: if outcome is not known or not reported

12.4 Adverse Event Monitoring and Assessment

Subjects will be monitored for AEs throughout the clinical investigation from signing the ICF until the final visit. Should an SAE occur after the final visit, which is considered at least possibly related to the IMD or procedure, such events should always be reported to Croma-

Pharma GmbH or its representative, even after the end of the clinical investigation.

Subjects will be questioned concerning their well-being at all visits from screening through to

the final visit. Furthermore, subject diaries will be provided to the subjects, and they will be

instructed to note Injection site reactions, AEs and AESI. In addition, subjects will be

encouraged to spontaneously report any AEs, ADEs or SAEs. Any subject with an AE, SAE or

clinically significant abnormal test result will be evaluated by the treating investigator and will

be treated and/or followed up as per local clinical practice. A physician, either at the

investigative site or at a nearby hospital emergency room, will administer treatment for any

SAEs. Where appropriate, medical tests and examinations may be performed to ensure that an

AE has fully resolved.

If an Injection site reaction is not resolved at the time the by the time the diary is returned after

4 weeks (after treatment, touch-up treatment, retreatment), the injection site reaction might be

classified as an AE s per investigator discretion.

By default, AEs ongoing at the termination visit will not be followed-up. However, SAEs which

are ongoing at the End of Clinical investigation visit will be followed-up until recovery or

normalization of changed laboratory parameters, or until the treating investigator determines

that the subject's condition is stable or a plausible explanation has been provided, whichever

occurs first.

All subjects excluded from repeat-treatment should continue to be followed until the resolution

of all ongoing AEs, regardless of device relatedness.

Adverse events will be coded using the current version of the Medical Dictionary for Regulatory

Activities (MedDRA). Whenever possible, a specific disease or syndrome, rather than

STRICTLY CONFIDENTIAL

CPH-301-201200F

individual associated signs and symptoms, should be identified by the treating investigator and recorded on the CRF. However, if an observed or reported sign or symptom is not considered a component of a specific disease or syndrome by the treating investigator, it should be recorded as a separate AE on the CRF

When documenting AEs, standard medical terminology should be used in order to avoid the use of vague, ambiguous, or colloquial expressions. Each AE will be evaluated by the treating investigator for:

- Seriousness, as defined in Section 12.1.
- Severity, as defined in Section 12.3.2.
- Causal relationship to IMD or procedure, as defined in Section 12.3.1.
- Outcome, as defined in Section 12.3.3.

If the severity rating for an ongoing AE changes before the event resolves, the AE will be reported in an additional row in the AE log (or additional AE page) with complete information (i.e. start and stop date, severity, relationship, outcome etc.).

Reporting Serious Adverse Events All SAEs for all subjects occurring from the time of informed consent until the End of Clinical investigation visit must be reported to Croma-Pharma GmbH or their representative within 24 hours of knowledge of the occurrence. If considered at least possibly related to clinical investigation treatment, SAEs observed after the End of Clinical investigation must also be reported.

SAE Report Forms must be completed and faxed to the Safety department within 24 hours of awareness of the event.

will inform the sponsor about all SAEs without undue delay after receipt of the respective report from the treating investigator.

STRICTLY CONFIDENTIAL

15 Mar 2021

Reporting to IRBs and regulatory authorities will follow pertinent national legislation.

Any details about AE reporting and casuality assessement are described in the current valid version of device safety management plan.

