- If the start date is completely missing, an AE will be considered treatment-emergent unless the stop date is before study product administration.

Device-related TEAEs/ TEADEs are defined as TEAEs/ TEADEs with possible or probable or definite relationship to study device.

Treatment-emergent AEs and ADEs will be summarized using the latest version of Medical Dictionary for Regulatory Activities (MedDRA) by System Organ Class (SOC) and Preferred Term (PT), classified from verbatim terms. The incidence and percentage of participants with at least 1 occurrence of a PT will be included, according to the most severe grade using a 3-point scale (mild, moderate, severe). The number of events per PT will also be summarized. Causality (relationship to study treatment) will be summarized separately.

The number and percentage of subjects as well as number of events will be presented for the treatment-emergent AEs and ADEs summaries. For summaries by SOC and PT, a subject will be counted once at the SOC level and once at each PT within the SOC level. For summaries by SOC, PT, and maximum severity, a subject is counted once at the highest severity level for which the event occurred at the SOC level and the highest severity level for each unique PT within that SOC level. Therefore, subjects may only contribute once to each PT and once to each SOC level.

Only injection site reaction AEs will be summarized by treatment group. However all AEs will be summarized by overall for both treatment groups together.

This document is confidential.

The incidence and frequency of treatment-emergent AEs, ADEs, SAEs, SADEs, and special interest AEs will be summarized by treatment group for injection site reaction AEs, and all AEs will be summarized by overall according to SOC and PT. AEs and ADEs will also be listed. The duration of AEs and ADEs will be determined and included in listings, along with the action taken and outcome.

Summaries presenting frequency of treatment-emergent AEs/ ADEs by SOC and PT will be ordered by overall descending frequency of SOC and then, within a SOC, by overall descending frequency of PT.

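### Protocol 12.2 and 12.4 give opposite rules for recording an AE whose severity changes, and SAP 9.3 counts events without defining an event or merging the extra rows

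*Protocol*

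**What the plan says.** Protocol 12.2 (Documentation of Adverse Events) covers an AE whose severity or seriousness changes. It says that "the most severe intensity or seriousness of the AE will be recorded and included in the analysis", and adds: "Separate AEs will not be recorded for each intensity level".

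Protocol 12.4 (Adverse Event Monitoring and Assessment) covers the same situation. When the severity of an ongoing AE changes before it resolves, "the AE will be reported in an additional row in the AE log (or additional AE page) with complete information". The added row, or added AE page, is a full record with its own dates, severity, causality and outcome.

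SAP 9.3 takes AE data to both subject-level and event-level output. On events it says "The number of events per PT will also be summarized" and, more generally, "The number and percentage of subjects as well as number of events will be presented for the treatment-emergent AEs and ADEs summaries". Its only collapsing rule concerns subjects: "subjects may only contribute once to each PT and once to each SOC level". It also derives a duration for each AE, for use in listings. The SAP table index has an AE table by maximum severity (14.3.1.3.1.1) and a separate one by severity (14.3.1.3.1.2).

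**The concern.** The two protocol sections share a trigger and prescribe opposite actions. An AE that goes from mild to moderate and back to mild is one record under 12.2 and three under 12.4. Nothing in SAP 9.3 tells the programmer which structure to expect, or what to do if both are present because sites followed different sections.

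The frequency and severity of AEs are stated safety outcomes (Protocol 7.3.2, SAP 3.4). If rows are counted as events, the number of events in a table would depend partly on which paragraph a site followed. SAP 9.3 splits AE summaries by device only for injection site reaction AEs, so event counts in that comparison are among the affected output.

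Protocol 12.4 also fits poorly with the outcome categories in Protocol 12.3.3, which have no entry for a change of severity. The earlier row would need a stop date with either a resolved outcome, which would be untrue, or an ongoing outcome, which contradicts the stop date.

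**Working it through.** The plan states no figure on this point, so there is none to reproduce. The check compares the texts and then works out the size by simple arithmetic.

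**Step 1. One AE under each rule.** Take a single AE in one subject on one side: mild from d0, moderate from d1, mild again from d2, resolved at d3.

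| Output | Protocol 12.2 | Protocol 12.4, rows counted as events |
|---|---|---|
| Records | 1 | 3 |
| Events for the preferred term | 1 | 3 |
| Subjects for the preferred term | 1 | 1 |
| Subject's maximum severity | moderate | moderate |
| Listed duration | one span, d0 to d3 | three shorter spans |
| Events by severity grade, if that table shows events | 1 moderate | 2 mild, 1 moderate |

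The subject rows agree because SAP 9.3 counts a subject once per system organ class and preferred term, at the highest grade. The event and duration rows differ because no equivalent rule exists for events.

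**Step 2. Size.** Let q be the share of AEs whose severity changes before resolution, and k the mean number of changes in those AEs. Under 12.4, an AE with no change gives 1 row and an AE with changes gives on average 1 + k rows. Therefore

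rows per true AE = (1 − q)·1 + q·(1 + k) = 1 + q·k.

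The documents give neither q nor k. For 100 true AEs, under assumed values:

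- q = 5%, k = 1: 100 × (1 + 0.05) = 105
- q = 10%, k = 1: 100 × (1 + 0.10) = 110
- q = 20%, k = 1: 100 × (1 + 0.20) = 120
- q = 20%, k = 2: 100 × (1 + 0.40) = 140

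Under 12.2 the count is 100 throughout. If only some sites followed 12.4, the overall factor lies between 1 and these values.

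**Step 3. Does another part of the documents settle it?** Protocol 12.2 says that the worst grade goes into the analysis, which points towards one event per AE. SAP 9.3 does not carry that into its event counts. Protocol 12.4 refers AE reporting details to a device safety management plan, and SAP section 18 refers to a separate shells document. Neither is available here, so a merging rule could exist in one of them but cannot be confirmed.

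**The case against.** The strongest reply is that inflation does not follow from the text. Protocol 12.4 speaks of the same AE being given another row, not of a new AE. Protocol 12.2 already says that the worst intensity is what is analysed. A programmer who reads both would join the rows, and no passage says that a row is an event. This part stands: a reader might infer that event counts are inflated wherever 12.4 was followed, and the documents do not support that without the further condition that rows are counted as events. What remains is that the SAP leaves the choice open, and a 12.4 row with its own dates and outcome looks like a separate AE in the dataset.

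A reader might also infer a bias between the devices. The documents do not support that either. Each subject receives both devices at one site, so that site's recording habit applies to both sides of the face. A difference would arise only if severity changed more often with one device. No hypothesis test uses event counts, and the confirmatory hierarchy contains effectiveness endpoints only.

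Three further limits are fair:

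- Many short-lived injection site reactions are captured in the diary. SAP 9.3 summarizes them separately, by subject and maximum severity. They reach the AE log only if they persist and the investigator so decides, so many grade changes may never meet the 12.4 rule.
- AE durations are listed rather than summarized, and a reader of an ordered listing could spot adjoining rows.
- The SAP indexes no AE table by site, so differences in recording between sites would not be displayed directly, although they would still enter the pooled counts.

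**Conclusion.** The contradiction between Protocol 12.2 and 12.4 is established from current text, as is the absence from SAP 9.3 of a definition of an event or a merging step. The consequence is conditional: 12.4 must have been followed for some AEs, and their rows must be counted as events. Then event counts rise by 1 + q·k. The factors of 1.05 to 1.40 illustrate assumed inputs; they are not estimates of what happened in this trial. The effect is confined to event counts overall and per preferred term, any event counts in Table 14.3.1.3.1.2, and listed durations. Numbers and percentages of subjects, maximum-severity tables and the effectiveness analyses do not change. It should be corrected before the safety tables are run, but it does not bear on the non-inferiority conclusion.

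**What to change.** Reconcile Protocol 12.2 and 12.4 to a single recording rule. On its own this will probably change little: the protocol anticipated the last visit in Q3 2021 and the SAP cites shells dated 15 August 2022, so most AEs will already have been recorded.

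The useful change is in SAP 9.3. Define an event, and state that before events are counted or durations derived, rows with the same subject, side and term are merged into one event when one row's start date adjoins the previous row's stop date. The merged event takes the maximum severity and runs from the first start to the last stop. This carries out the analysis rule already in 12.2 and works whichever section a site followed. The text should also say what counts as adjoining (for example, the same or the next calendar day), how incomplete dates are treated, that AEs with side not applicable are merged among themselves, and that the merged event takes the strongest causality, the worst seriousness and the last recorded outcome.

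The cost is one protocol sentence and one SAP derivation, with no new data. Reporting the number of rows merged would show whether the issue mattered in practice.
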